
Statistical Methods
	
In Cohort 1, approximately 52 evaluable patients may be enrolled and treated with glembatumumab vedotin monotherapy with objective response rate (ORR) as the primary endpoint. As patients who discontinue study prior to the first disease assessment for reasons unrelated to study treatment will be excluded from the response-evaluable population, it is anticipated that approximately 60 patients will be enrolled in this cohort. For Cohort 1, the sample size was determined to estimate the ORR with one-sided significance level of 5% and power of 80%, using exact binomial test, to determine if the ORR exceeds a predefined minimum. A sample size of 52 patients will test the null hypothesis of an ORR of 5% versus 15% under the alternative hypothesis. If the number of responses (CR or PR) is 6 or more, the null hypothesis will be rejected with the actual error rate of 0.045. If the number of responses is 5 or less, the alternative hypothesis will be rejected with an actual error rate of 0.188.
 
For Cohorts 2, 3, and 5, ORR by RECIST 1.1 remains the primary endpoint. Supplementary analyses of tumor response and progression may also be performed for Cohorts 2-5 using irRECIST criteria (in which new lesions do not necessarily constitute progression, but contribute to the calculated sum of diameter of all measurable disease) (Nishino, Giobbie-Hurder et al. 2013).
 
For Cohorts 2, 3, and 5, approximately 30 patients per cohort, to achieve 25 evaluable, will be enrolled to have the maximum width of the 95% confidence interval (CI) of the estimated ORR to be no greater than 41%. If 7, 8, or 9 responses are observed (i.e., the estimated ORR is 28%, 32%, or 36%) among the 25 evaluable patients, then the lower limits of the two-sided 95% CIs of the estimated ORR are 12%, 15%, and 18%

respectively. These calculations are based on the Clopper-Pearson method for exact confidence intervals. As a secondary consideration, 25 evaluable patients can achieve 90% power for ORR of 25% comparing to 5% and 79% power comparing to 10% ORR with 1-sided type I error of 0.1 based on exact binomial test.

Cohort 4 will enroll approximately 10-12 patients for safety and tolerability assessment of glembatumumab vedotin and CDX-301. Pre- and on-study tumor biopsies will be analyzed for the effect of CDX-301 on the tumor microenvironment, including the effect on intratumoral dendritic cell populations. The anti-tumor activity will also be explored as a secondary endpoint.

Patients in Cohorts 2-5 who experience an event determined to be a treatment-limiting toxicity will not be replaced and will be considered evaluable.

All statistical analyses will be performed separately for each treatment cohort, unless specified differently. Given the timing of different cohorts, statistical analyses will be performed for each cohort when sufficient data is available upon completion of enrollment.

ORR will be estimated as the proportion of patients who achieve best overall response of CR or PR per RECIST 1.1 that are confirmed at an interval of at least 28 days. Secondary analyses of ORR will include responses observed at a single-time point. The final analysis of ORR will be based on the investigator assessment of response. However, in the event of a positive study outcome, an additional assessment of ORR may be performed by an independent review committee (IRC). The estimate of the objective response rate will be accompanied by one- and two-sided exact 95% Clopper-Pearson confidence interval for each cohort. In addition, one-sample exact binomial test will be used to test the null hypotheses of ORR (Cohort 1: $ORR \leq 5\%$; Cohorts 2, 3, and 5: both $ORR \leq 5\%$, and $ORR \leq 10\%$) with one-sided significance level of 0.05 for Cohort 1 and 0.1 for Cohorts 2, 3, and 5. The primary ORR analyses will be based on respective evaluable population and the secondary analysis will be based on respective ITT population. Supplementary analyses of tumor response and progression may also be performed using irRECIST criteria (in which new lesions do not constitute progression, but contribute to the calculated sum of diameter of all measurable disease). Exploratory analysis will be performed for comparing the three cohorts on efficacy endpoints, and no adjustment for multiple testing will be considered.

Waterfall plots will be used to depict graphically the maximum decrease from baseline in the sum of longest diameters of target lesions. Correlation between the degree of gpNMB expression and maximum decrease from baseline in the sum of longest diameters of target lesions will be evaluated. For this analysis, all patients will be used, with gpNMB expression measured on a continuous scale (percentage of gpNMB-positive tumor cells). Further, to explore the predictive power of various cut-off values for gpNMB expression, a receiver operating curve (ROC) analysis for the response data ([Gönen and SAS Institute. 2007](#)) will be performed.

The duration of objective response, PFS, and OS will be summarized descriptively for all patients, using the Kaplan-Meier method. The association between the degree of gpNMB expression and PFS will be evaluated using a Cox proportional hazards model. For this analysis, all patients will be used, with gpNMB expression measured on a continuous scale (percentage of gpNMB-positive tumor cells). When a factor is continuous, the hazard ratio is interpreted as the change in risk for each 1-unit increase in the factor. For example, a hazard ratio of 0.99 indicates the hazard for the event decreases by 1% for each 1%-unit increase in gpNMB expression level. For Cohort 1, if a true hazard ratio of 0.99 is assumed and the standard deviation for gpNMB expression level is $\pm 35\%$, 36 PFS events from among the 52 evaluable patients (70% event rate)

	
will provide approximately 80% power with one-sided significance level of 10% (Hsieh and Lavori 2000). The predictive power of various cut-off values for gpNMB expression will be explored based on a receiver operating curve (ROC) analysis for censored data (Gönen and SAS Institute. 2007). Similar analyses will be performed for Cohorts 2, 3, and 5 separately.
 
For the above analyses, the most recent tumor sample will be utilized to determine the tumor gpNMB expression level for each patient. Additional exploratory analyses may be performed to examine the distribution and intensity of gpNMB expression (i.e., staining intensity and percentage of positive tumor and stromal cells) relative to outcome, as well as comparison of Historic and Pre-Study samples to determine whether gpNMB expression changes over time and/or with specific prior therapies.

--	--

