Patients will receive study treatment in an open-label fashion. Approximately 60 patients were enrolled and received glembatumumab vedotin in Cohort 1. Approximately 30 patients were enrolled in Cohort 2 and received glembatumumab vedotin in combination with varlilumab. Approximately 30 patients will be enrolled in the glembatumumab vedotin and a PD-1 targeted CPI combination Cohort 3. Cohorts 2 and 3 enrolled patients in parallel. Approximately 10-12 patients will be enrolled in Cohort 4 (glembatumumab vedotin in combination with CDX-301) and, if the data is supportive in Cohorts 3 and 4, approximately 30 patients will be enrolled in Cohort 5 (glembatumumab vedotin in combination with both CDX-301 and a PD-1 targeted CPI).

Cohort	Treatment	Glembatumumab Vedotin Dose	Varlilumab Dose	Patients (n)
1	Glembatumumab vedotin	1.9 mg/kg	-	Approx. 60
2	Glembatumumab vedotin + Varlilumab	1.9 mg/kg	3.0 mg/kg*	Approx. 30

Cohort	Treatment	Glembatumumab Vedotin Dose	PD-1 CPI Dose	CDX-301 Dose	Patients (n)
3	Glembatumumab vedotin + PD-1 targeted CPI**	1.9 mg/kg	As per institutional standard of care with reference to the package insert	-	Approx. 30
4	Glembatumumab vedotin + CDX-301**	1.9 mg/kg	-	75 µg/kg x 5 days	Approx. 10-12
5	Glembatumumab vedotin + CDX-301 + PD-1 targeted CPI**	1.9 mg/kg	As per institutional standard of care with reference to the package insert	75 µg/kg x 5 days	Approx. 30

*If >2 treatment-limiting toxicities occur in the first 10 patients, or in >20% of patients thereafter, all further patients enrolled will receive a varlilumab starting dose of 0.3 mg/kg and ongoing patients will also receive any further dosing of varlilumab at 0.3 mg/kg.

**If >2 treatment-limiting toxicities occur in the first 10 patients, or in >20% of patients thereafter, then enrollment in Cohorts 3-5 will be interrupted pending evaluation by Celldex and the investigators.

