Continuous evaluation of toxicity will be performed by the investigators and Celldex throughout the entire course of patient treatment. Treatment-limiting toxicity (as defined in [Section 8.7](#)) will be reported to Celldex within 24 hours, and site teleconferences between Celldex and all participating sites will be held at frequent intervals to evaluate emerging safety data. In Cohort 2, if treatment-limiting toxicity occurs in >2 of the first 10 patients, or in $>20\%$ of patients thereafter, all further patients enrolled will receive a varlilumab starting dose of 0.3 mg/kg and ongoing patients will also receive any further dosing of varlilumab at 0.3 mg/kg. If additional treatment-limiting toxicity occurs in $>20\%$ of patients receiving varlilumab at 0.3 mg/kg, enrollment will be interrupted pending evaluation by Celldex and the investigators. In Cohort 3-5, if treatment-limiting toxicity occurs in >2 of the first 10 patients or in $>20\%$ of patients thereafter, then enrollment for the entire cohort will be interrupted pending evaluation by Celldex and the investigators. The FDA and site IRBs will be notified of the analysis and determination regarding further enrollment. Enrollment in Cohort 5 will not commence until the evaluation of toxicity and activity in Cohorts 3 and 4 of all treated patients has been assessed and it has been determined that the combinations of glembatumumab

vedotin with CDX-301 and glebatumumab vedotin with PD-1 targeted CPI are safe and tolerable.

Treatment-Limiting Toxicity (TLT) Definition

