Continuous evaluation of toxicity will be performed by the investigators and Celldex throughout the entire course of patient treatment. Treatment-limiting toxicity (as defined in Section 8.7) will be reported to Celldex within 24 hours, and site teleconferences between Celldex and all participating sites will be held at frequent intervals to evaluate emerging safety data. In Cohort 2, if treatment-limiting toxicity occurs in >2 of the first 10 patients, or in >20% of patients thereafter, all further patients enrolled will receive a varlilumab starting dose of 0.3 mg/kg and ongoing patients will also receive any further dosing of varlilumab at 0.3 mg/kg. If additional treatment-limiting toxicity occurs in >20% of patients receiving varlilumab at 0.3 mg/kg, enrollment will be interrupted pending evaluation by Celldex and the investigators. In Cohorts 3-5, if >2 of the first 10 patients experience treatment-limiting toxicities, or in >20% of patients thereafter, then enrollment in the cohort will be interrupted pending evaluation by Celldex and the investigators. The FDA and site IRBs will be notified of the analysis and determination regarding further enrollment. Enrollment in Cohort 5 will not commence until the evaluation of toxicity and activity in Cohorts 3 and 4 of all treated patients has been assessed and it has been determined that the combinations of glembatumumab vedotin with CDX-301 and glembatumumab vedotin with PD-1 targeted CPI are safe and tolerable.

For all cohorts, study analyses will include a retrospective assessment to define the range of gpNMB expression for all enrolled patients and to determine if outcome correlates with intensity or distribution of gpNMB expression. In Cohorts 2 and 3, normal skinfold biopsies are collected prior to study entry for retrospective assessment to identify patients predisposed to rash. Skinfold biopsies will be collected until such time Celldex informs the sites that further data is not needed.

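### The treatment-limiting toxicity (TLT) trigger counts toxicities in the synopsis footnotes but patients in the synopsis text and Sections 7.1 and 8.6.2, so the same data can interrupt enrollment under one and not the other

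*Protocol*

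**What the plan says.** The trigger appears in four places in the Protocol.

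- **Synopsis dose-table footnotes.** For Cohorts 3-5: "If >2 treatment-limiting toxicities occur in the first 10 patients, or in >20% of patients thereafter, then enrollment in Cohorts 3-5 will be interrupted". For Cohort 2: "If >2 treatment-limiting toxicities occur in the first 10 patients, or in >20% of patients thereafter, all further patients enrolled will receive a varlilumab" dose at the lower level. Both count toxicities in the first limb.
- **Synopsis, overview of study design.** For Cohort 2: "In Cohort 2, if treatment-limiting toxicity occurs in >2 of the first 10 patients". For the later cohorts: "In Cohort 3-5, if treatment-limiting toxicity occurs in >2 of the first 10 patients", and the consequence is "then enrollment for the entire cohort will be interrupted pending evaluation by Celldex and the investigators".
- **Section 7.1.** The patient count again: "In Cohorts 3-5, if >2 of the first 10 patients experience treatment-limiting toxicities", with the consequence "then enrollment in the cohort will be interrupted pending evaluation by Celldex and the investigators". The Cohort 2 wording matches the synopsis text.
- **Section 8.6.2.** Cohort 2 only, also by patients.

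The second limb, more than 20% thereafter, refers to patients in all four places. None says which wording governs, and the SAP does not restate the rule.

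**The concern.** A safety trigger should give one answer for one data set. Here the answer depends on the page consulted whenever an affected patient has more than one TLT.

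Section 8.7 allows that. TLTs are reportable at any time during treatment. In Cohorts 3-5, a related toxicity that warrants stopping any one of the agents is a TLT. A patient who stops the PD-1 inhibitor or CDX-301 may stay on glembatumumab vedotin, and can then have a second TLT from that drug.

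In the text available, this is the only numerical cohort-level safety trigger for Cohorts 3-5, and safety is the primary objective of Cohort 4.

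**Working it through.** **Inputs.** From the Protocol: a threshold of more than 2 in the first 10; the unit is toxicities (footnotes) or patients (elsewhere); the second limb is more than 20% of patients everywhere. The documents give no trigger probability, so there is no figure to reproduce. Assumed here: per-patient TLT risk p, and a share q of affected patients who have exactly two TLTs.

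**Step 1. Apply both versions to the same first ten patients.**

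| TLTs | Patients affected | Footnote (TLTs > 2) | Text (patients > 2) |
|---|---|---|---|
| 3 | 3 | triggers | triggers |
| 3 | 2 | triggers | does not |
| 4 | 2 | triggers | does not |

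The 20% limb does not close the gap, because 2/10 = 20% is not above 20%. With at most one TLT per patient the versions agree.

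**Step 2. How often they would part.** Let X be binomial (10, p).

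- Patient count: P(X ≥ 3). At p = 0.10 this is 1 − 0.349 − 0.387 − 0.194 = 0.070.
- Event count: both versions trip when X ≥ 3, and X = 1 gives at most two TLTs. The only addition is X = 2 with at least one repeat: P(X = 2) × [1 − (1 − q)²], where P(X = 2) = 45 × 0.1² × 0.9⁸ = 0.194.

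| q | Addition at p = 0.10 | Event-count probability |
|---|---|---|
| 0% | 0 | 0.07 |
| 5% | 0.194 × 0.0975 = 0.019 | 0.09 |
| 10% | 0.194 × 0.19 = 0.037 | 0.11 |
| 20% | 0.194 × 0.36 = 0.070 | 0.14 |
| 50% | 0.194 × 0.75 = 0.145 | 0.22 |

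At p = 0.20 the patient count gives 0.32; the event count gives 0.38, 0.43 and 0.55 for q = 10%, 20% and 50%.

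**Step 3. Scope.** Suppose 3 of the first 10 patients in Cohort 3 and none of the first 10 in Cohort 4 have a TLT. Section 7.1 interrupts Cohort 3 only. A literal reading of the footnote interrupts Cohort 4 as well. If both cohorts enroll together and are independent, at p = 0.10 a given cohort is stopped with probability 0.070 on its own data. If either cohort's breach stops both, the probability is 1 − (1 − 0.070)² = 0.135.

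**Step 4. Can repeats occur in Cohort 2?** Section 8.6.2 has a Cohort 2 patient with a TLT stop all study treatment, glembatumumab vedotin included. Section 8.7 lets a patient who stops varlilumab continue glembatumumab vedotin. Under the former, repeats would be mainly concurrent events; under the latter, later ones are possible. This is a second contradiction, and it bears on the first.

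**The case against.** The footnotes can be taken as shorthand for the text, since their own second limb is in patients. Repeat TLTs should also be limited. In Cohorts 3 and 5, stopping glembatumumab vedotin ends the study treatment phase; in Cohorts 4 and 5 it also ends CDX-301, which is given only as two five-day courses. A later second TLT mostly needs another agent to be stopped first. Nothing in the documents supports any particular repeat rate. The consequence for Cohorts 3-5 is a pause for evaluation, alongside 24-hour reporting and continuous toxicity review. All of this stands. It makes the low end of the table more plausible, but it does not make the wordings agree.

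A reader might infer more than the documents support:

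- *That the rule is stated in three ways.* The synopsis text and Section 7.1 agree in substance, and Section 8.6.2 matches them for Cohort 2. There are two versions.
- *That the scope conflict is certain.* The footnote mark is attached to each of the Cohort 3, 4 and 5 rows, so it can mean each cohort in turn. Scope matters only where cohorts enroll together. Cohort 5 opens only after Cohorts 3 and 4 are evaluated, and no overlap of Cohorts 3 and 4 is stated.
- *That the wording on later patients is contradictory.* It is the same everywhere. It leaves open whether the 20% is cumulative or only among patients after the tenth, which is an ambiguity.
- *That the Cohort 2 dose still turns on this.* Cohort 2 is already enrolled in this version, so its first-ten limb is largely retrospective.
- *That the opening of Cohort 5 hinges on the TLT count.* No passage says so; it rests on a review of toxicity and activity in all treated patients of Cohorts 3 and 4.

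**Conclusion.** The contradiction in the unit of count holds on the text. Two versions of one safety trigger give opposite actions on the same first ten patients when at least one of two affected patients has more than one TLT. At an assumed 10% risk per patient, the trigger probability moves from 0.07 to between 0.09 and 0.22 for repeat rates of 5% to 50%. At a repeat rate of zero there is no difference. These rates are assumptions, so the probabilities show scale and are not forecasts.

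The scope difference is a matter of reading, but the literal reading carries a real consequence if Cohorts 3 and 4 overlap. The forward effect is on Cohorts 3-5. How far it reaches Cohorts 4 and 5 in practice cannot be told from these documents, because the SAP covers Cohorts 1-3 only. No view is taken on which rule is right.

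**What to change.** Reconcile the synopsis footnotes with the synopsis text, Section 7.1 and Section 8.6.2, so that each states:

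- the same unit of count: patients with at least one TLT, or TLT events;
- the same scope: the affected cohort, or Cohorts 3-5 together;
- the denominator for the 20% limb: all patients so far, or only those after the tenth.

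In the same edit, reconcile Sections 8.6.2 and 8.7 on whether a Cohort 2 patient continues glembatumumab vedotin after a TLT. The sponsor chooses the rule in each case. The cost is amendment wording, with no added patients or data.

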4. SCHEDULE OF ASSESSMENTS

Table 1: Schedule of Assessments (Cohorts 1-3)

Visit	Screening ²	Treatment Visits ³						Disease Assessment Visit ⁵ Every 6 (±1) weeks for 6 months then every 9 (±2) weeks thereafter	Survival Assessment ⁶ Every 12 (±2) weeks until study closure
		Cycle 1/ Day 1	Cycle 1/ Day 7 (Cohorts 2 and 3)	Cycle 1/ Day 14 (Cohorts 2 and 3)	Cycle 2/ Day 1	Cycle 3, 4, 5, etc./ Day 1	End of Treatment ⁴		
Visit window¹	Day -28 to Day -1		+/- 1 day	+/- 1 day	+/-3 days	+/-3 days	Within 28 days post-dosing		
Informed Consent, and, if applicable, HIPAA	X								
Tumor tissue ⁷	X ⁸	X ⁹							
Skin fold biopsy ⁷	X ⁸								
Medical history ¹⁰	X	X							
Physical examination ¹¹	X	X ¹²			X	X	X		
Vital signs ¹³	X	X			X	X	X		
ECOG performance status	X	X ¹²			X	X	X		
Electrocardiogram (ECG)	X						X		
Pregnancy test ¹⁴	X	X ¹²							
Hematology ¹⁵	X	X ¹²	X	X	X	X	X		
Blood chemistry ¹⁵	X	X ¹²	X	X	X	X	X		
Urinalysis/dipstick ¹⁵	X	X ¹²					X		
Thyroid function test (Cohort 2) ¹⁵	X	X ¹²				X (Odd cycles)	X		
Immunogenicity ^{16, 17}		X				X (Odd cycles)	X		
PBMC collection ^{17, 18}		X			X	X (Cohorts 2 and 3, Cycle 5 only)			
PK sample collection ^{17, 19}		X			X	X (Odd cycles)	X		
PD sample collection ¹⁷		X			X		X		
Disease assessment ²⁰	X							X	
Administration of glembatumumab vedotin ²¹		X			X	X			
Administration of varlilumab ²² (Cohort 2)		X			X	X ²¹			
Administration of PD-1 targeted CPI (Cohort 3) ²³		X	X ²³						
Survival status								X	
Concomitant medication review ²⁴	X	X	X	X	X	X	X	X	X
Adverse event monitoring ²⁵		X	X ²⁶	X ²⁶	X	X	X	X ²⁷	X ²⁷

(footnotes on next page)

Table 1 - Footnotes:

1. A delay in study treatment or performance of study visits due to holidays, weekends, inclement weather or other unforeseen circumstances will be permitted and not considered a protocol violation. However, significant delays (i.e., greater than one week) due to these reasons should be discussed with the study medical monitor to reach consensus on subsequent scheduling. See (Section 8.6) and (Section 8.8) for management of dosing delays due to toxicity.
2. Informed consent may be signed at any time prior to or during the screening period. No study-specific procedures will be performed prior to receipt of signed Informed Consent. However, assessments performed according to standard of care prior to receipt of Informed Consent may be utilized to fulfill the screening requirement, if completed within the required window for screening.
3. Patients will receive study treatment until intolerance, progression of disease, or any of the other criteria for discontinuation of study treatment (Section 7.2.4.1.1) are met. All cohorts will receive glembatumumab vedotin on a three-week cycle. Cohort 2 patients will also receive varlilumab on Day 1 of Cycles 1, 2, 4, 6, 8, and 10. Cohort 3 patients will also receive a PD-1 targeted CPI per institutional standard of care.
4. The End of Treatment Visit should be performed within 28 days after last dose of study treatment and prior to initiation of alternate therapies.
5. Disease assessments will be performed every 6 weeks (± 1 week) for 6 months and every 9 weeks (± 2 weeks) thereafter, scheduled based on the first dose of glembatumumab vedotin at C1D1, until documented progression of disease or initiation of alternate anticancer therapies. For Cohorts 2 and 3, in cases of apparent progression that may reflect enhanced inflammation and/or an initial imbalance in the kinetics of tumor growth and anti-cancer immune activity, continued combination treatment may be allowed with permission granted from the Celldex Medical Monitor, until a second radiologic confirmation of progression performed at the next scheduled disease assessment (or sooner if clinically indicated) (Section 5.6.4 and Section 7.2.4.1.1). If a partial or complete response is noted, a follow-up disease assessment must be done no sooner than 28 days later to confirm response. Patients who discontinue treatment in the absence of progression will continue to have tumor assessments until documented progression or initiation of alternate anti-cancer therapies. If surgical intervention or localized radiation are indicated (either for palliation or down-staging of previously non-resectable tumor), these interventions should be avoided if clinically feasible until after the 12 week response assessment. Prior to any intervention (such as surgical resection, palliative radiation or alternate anti-cancer therapy), every effort should be made to perform a tumor response assessment in order to document progression and/or confirm an objective response. Patients who undergo surgical resection or radiation in the absence of progression may continue to receive study treatment until remaining lesions meet criteria for progression of disease.
6. Subsequent to disease progression, all patients will be followed at 12 (± 2) week intervals until study closure. Patients who discontinue treatment in the absence of progression will continue to have tumor assessments until documented progression or initiation of alternate anti-cancer therapies. These visits may be performed by telephone.
7. Assessment of gpNMB expression will be performed by IHC, retrospectively, at a central laboratory on FFPE Historic and Pre-entry (tumor and skin fold [axilla or groin] biopsy) samples. Skin biopsy should be 3-5 mm in diameter. Additional analyses performed centrally may also include, but are not limited to, gpNMB expression by Reverse Transcriptase Polymerase Chain Reaction (RT-PCR), examination of tumor markers using IHC or other molecular analyses, evaluation of tumor infiltrating leukocyte populations, biomarkers related to immune activation and localization of glembatumumab vedotin, CR011, or MMAE at the tumor site in post-treatment samples. Sample collection, processing and shipping instructions will be provided separately.
8. Historic FFPE samples must represent the advanced stage of disease (Stage III or IV). Pre-entry FFPE samples must be obtained within 12 weeks prior to study entry, be subsequent to the last systemic anticancer therapy received, and be post-tumor progression. For patients who must undergo biopsy to obtain a FFPE Pre-entry sample, biopsy sites must be soft tissue tumor or visceral lesions that can be biopsied with acceptable clinical risk (as judged by the investigator). The biopsy site chosen should not have been previously irradiated and must be distinct from RECIST 1.1 target lesions. Tissue from multiple previous collection dates should also be submitted, when available/feasible, in order to further understand how gpNMB levels may change over time and/or with cancer stage. Skin biopsies (Cohorts 2 and 3) must be obtained within 12 weeks of study entry.
9. At recurrence, biopsy and central analysis of recurrent tumor is optional but strongly encouraged. Similarly, in the event of tumor resection or biopsy performed per standard of care anytime during treatment or following tumor progression, submission of these tissue samples for central analysis is strongly encouraged.

10. Medical history includes demography, melanoma history, previous surgeries/therapy, and pre-existing diseases. At Cycle 1, Day 1, medical history is updated prior to administration of study drug.
11. Complete physical exam should be performed at screening; thereafter, symptom-directed exams are acceptable.
12. Assessments do not need to be repeated if completed within the previous 24 hours as part of the screening assessment.
13. Vital signs to include height (at screening only), weight, respiration, pulse, temperature, and resting systolic and diastolic blood pressure. In Cohort 2 on glembatumumab vedotin and varlilumab dosing days, vital signs should be assessed pre-infusion, at 45 (±15) minutes during each infusion, and within one-half hour following completion of each infusion. In Cohort 3, vital signs should be assessed for each glembatumumab vedotin infusion as follows: pre-infusion, at 45 (±15) minutes during the infusion, and within one-half hour following completion of the glembatumumab vedotin infusion. Additionally, when the PD-1 targeted CPI is administered with or without glembatumumab vedotin dosing, vital signs should be assessed prior to each PD-1 targeted CPI infusion and additionally, as necessary, per clinical and institutional standards. (Note: weight is only assessed once per visit.)
14. Serum or urine pregnancy test only for women of childbearing potential. Patients of non-childbearing potential include those who are ≥60 years, surgically sterilized, or postmenopausal with absence of menses for at least 1 year. However, women <60 with therapy-induced amenorrhea will require a pregnancy test unless additional evidence (oophorectomy or serial measurement of FSH and/or estradiol) are available to ensure postmenopausal status.
15. Laboratory assessments must include the following, when indicated. Hematology results must be reviewed prior to dosing. For patients in Cohort 2, liver function tests (i.e., ALT, AST, and total bilirubin) and creatinine must also be reviewed prior to dosing. In addition, in Cohort 2, thyroid function tests must be performed at screening, at Cycle 1, at every odd cycle (i.e., Cycles 3, 5, 7, etc.), and at End of Treatment.

Hematology:	Clinical Chemistry:	Urinalysis
Hemoglobin	Sodium	pH
Hematocrit	Potassium	Protein
Mean corpuscular volume (MCV)	Chloride	Glucose
Erythrocyte count (RBC)	Bicarbonate	Specific gravity
Leukocytes (WBC)	Glucose (nonfasting)	Blood
Platelets	Blood urea nitrogen (BUN)	
Differential:	Creatinine	Microscopic examination must be performed at baseline and, if clinically indicated, at subsequent visits (if urinary infection is suspected then a negative urine culture is required prior to enrollment.)
Neutrophils	Calcium	
Lymphocytes	Phosphate	
Monocytes	Alkaline phosphatase	
Eosinophils	Alanine transaminase (ALT/SGPT)	Thyroid Function Test (Cohort 2 only)
	Aspartate transaminase (AST/SGOT)	TSH
	Total protein	Free T4 and T3
	Albumin	
	Lactate Dehydrogenase (LDH)	
	Total Bilirubin	Free T4 and free T3 performed at screening, and then only if TSH is abnormal at subsequent visits.

Differential should be reported consistently throughout the study as either an absolute count (preferred) or as a percentage.

16. Samples for immunogenicity will be collected prior to dosing on Day 1 of “odd” cycles (i.e., Cycles 1, 3, 5, 7, etc.).
17. Analyses will be performed centrally. Sample collection, processing and shipping instructions will be provided separately.

18. For Peripheral Blood Mononuclear Cell (PBMC) collection on Cycle 1/Day 1 and Cycle 2/Day 1, samples are collected prior to dosing. For Cohort 1 an additional sample is collected at End of Treatment. For Cohorts 2 and 3 an additional sample is collected on Cycle 5/Day 1 prior to dosing. Analyses may include (but are not limited to) examination of gpNMB expression (and/or potential binding partners for gpNMB) on myeloid suppressor cells; peripheral leukocytes; circulating tumor cells; and other immune response cells of interest. Additional analysis may include response assessment to potentially relevant tumor antigens and analysis of myeloid derived suppressor cells. Details on sample collection and handling will be provided separately. PBMC samples will be collected until such time Celldex informs the sites that further data is not needed.
19. Cohort 1: On Day 1 of Cycle 1 and 2 only, glebatumumab vedotin PK samples will be collected prior to dosing and at end of infusion (at or within 30 minutes after completion of infusion). A PK sample will also be collected at the End of Treatment visits.
Cohort 2: On Day 1 of Cycles 1, 2, and 5, a total of three PK samples will be collected on each day for glebatumumab vedotin and varlilumab PK analysis. PK samples will be collected prior to dosing of varlilumab, at end of varlilumab infusion (at or within 10 minutes after completion of infusion), and at end of glebatumumab vedotin infusion (at or within 10 minutes after completion of infusion). On Day 1 of Cycles 3, 7, and subsequent odd cycles, only one PK sample will be collected prior to the first infusion. An additional sample should be drawn as soon as possible for any patients who experience an infusion reaction. A PK sample will also be collected at the End of Treatment visits.
Cohort 3: On Day 1 of Cycles 1, 2, and 5, a total of two PK samples will be collected on each day for glebatumumab vedotin PK analysis. PK samples will be collected prior to dosing of glebatumumab vedotin and at end of infusion (at or within 10 minutes after completion of infusion). On Day 1 of Cycles 3, 7, and subsequent odd cycles, only one PK sample will be collected prior to the first infusion. An additional sample should be drawn as soon as possible for any patients who experience an infusion reaction. A PK sample will also be collected at the End of Treatment visits.
For Cohorts 1, 2, and 3, analysis may also include circulating soluble gpNMB levels or other soluble molecules.
20. Imaging-based evaluation per RECIST 1.1 should be performed. Contrast-enhanced Computed Tomography (CT) of the chest, abdomen, and pelvis, as well as all other suspected disease sites is required. Magnetic Resonance Imaging (MRI) exams of the brain, abdomen, and pelvis can be performed in lieu of a CT; however, MRI exams of the chest are not recommended. In the event that a chest MRI is performed, a non-contrast chest CT is strongly recommended to evaluate the lung parenchyma. Brain and/or bone scans are required for any patients with a history of metastases to bone and/or brain or where symptomatology raises the suspicion for bone and/or brain metastases. Lesions identified on bone scans should be confirmed by a CT or MRI at baseline, and, if identified as target lesions due to soft tissue component, they should continue to be followed by the same methodology (i.e., CT or MRI scan). However, bone lesions followed as non-target disease may be subsequently followed by bone scans only. Lesions that cannot be imaged but are assessable by clinical exam may be assessed by color photography including a ruler (preferred method) or measured with calipers. Normally, all target and non-target disease sites should be evaluated at each assessment. However, for patients with non-target bone disease, bone scans need only be repeated every twelve to eighteen weeks, or more frequently if clinically indicated. The same method of assessment and the same technique should be used to characterize each identified and reported lesion at baseline and during follow-up. Target lesions selected for tumor measurements should be those where surgical resection or radiation are not indicated or anticipated.
21. Unless otherwise specified, all study assessments should be performed prior to administration of study treatment(s), and may be performed up to 24 hours prior to treatment administration if assessments remain within the specified visit window.
22. In Cohort 2, varlilumab and glebatumumab vedotin will be administered as separate infusions with a break of at least 30 minutes between infusions. Varlilumab should be infused over 90 (\pm 10) minutes and administered before glebatumumab vedotin, also infused over 90 (\pm 10) minutes. Varlilumab will be administered on Day 1 of Cycles 1, 2, 4, 6, 8, and 10 only. Patients in Cohort 1 should be monitored for at least 1 hour following the last administration of study drug to monitor for infusion reaction/cytokine release syndrome/hypersensitivity reaction. Patients in Cohort 2 should be observed on Cycle 1 Day 1 for at least 2 hours after the last study drug, and for at least 1 hour at all subsequent dosing visits. Infusions should be given in a monitored setting that has ready access to an intensive care unit in case of a severe infusion reaction.

23. Administration of the PD-1 targeted CPI should be continuous from the prior standard of care treatment regimen during which the most recent disease progression occurred. No more than 3 doses of nivolumab or 2 doses of pembrolizumab should be missed between the most recent disease progression and initiation of treatment on study. Day 1 of Cycle 1 occurs with the first dose of glembatumumab vedotin which is administered on the same day as the PD-1 targeted CPI. When both glembatumumab vedotin and the PD-1 targeted CPI are administered on the same day, the drugs will be administered as separate infusions. The PD-1 targeted CPI should be the first infusion and glembatumumab vedotin administered at least 30 minutes later as the second infusion. Patients in Cohort 3 should be observed on Cycle 1 Day 1 for at least 2 hours after the last study drug, and for at least 1 hour at all subsequent dosing visits. Infusions should be given in a monitored setting that has ready access to an intensive care unit in case of a severe infusion reaction. The PD-1 targeted CPI will be administered in combination with glembatumumab vedotin until disease progression (using study screening disease assessment as baseline reference) or intolerance.
- Additional clinic visits and monitoring (such as laboratory assessments) relevant to the administration of the PD-1 targeted CPI will be conducted in accordance with standard of care when appropriate. However, all CPI dosing and adverse events occurring between study visits will be documented in the eCRF.
24. All concomitant medication will be documented in the Case Report Form (CRF) if taken within 28 days prior to Study Day 1, and either (whichever occurs sooner): a) 28 days after last dose of study treatment or b) initiation of alternate anti-cancer therapy. In addition, all anti-cancer medications should be recorded throughout the duration of study follow-up.
25. For patients who develop grade 3 treatment-related rash and who provide appropriate consent, punch biopsies and photographs of the rash, as well as uninvolved skin, are strongly encouraged. Samples may be analyzed centrally; in these cases, collection, processing and shipping instructions will be provided separately.
26. Adverse event monitoring on Cycle 1 Day 7 and Cycle 1 Day 14 for patients in Cohorts 2 and 3 can be performed in person or by telephone to determine if the patient is experiencing any adverse events.
27. Events occurring >28 days after discontinuation of glembatumumab vedotin, >70 days after discontinuation of varlilumab (Cohort 2), or >70 days after discontinuation of the PD-1 targeted CPI (Cohort 3) are only reportable if both serious (SAE) and potentially treatment-related.

Table 2. Schedule of Assessments (Cohorts 4 and 5)

Visit	Screening ²	Treatment Visits ³							Disease Assessment Visit ⁵	Survival Assessment ⁶
		Cycle 1/ Day -6 to Day -2	Cycle 1 / Day 1	Cycle 1 / Day 7	Cycle 1 / Day 15-19	Cycle 2 / Day 1	Cycle 3, 4, 5, etc. / Day 1	End of Treatment ⁴		
Visit window¹	Day -35 to Day -7		+3/- 1 days	+/- 1 day		+3/- 1 days	+/- 3 days	Within 28 days post-dosing	Every 6 (±1) weeks for 6 months then every 9 (±2) weeks thereafter	Every 12 (±2) weeks until study closure
Informed Consent, and, if applicable, HIPAA	X									
Tumor tissue ⁷	X ⁸			X ⁸				X ⁹		
Medical history ¹⁰	X	X (Day -6 only)								
Physical examination ¹¹	X	X ¹²	X		X	X	X	X		
Vital signs ¹³	X	X	X		X	X	X	X		
ECOG performance status	X	X ¹²				X	X	X		
Electrocardiogram (ECG)	X							X		
Pregnancy test ¹⁴	X	X ¹²								
Hematology ¹⁵	X	X ¹² (Day -6 only)	X	X	X (Day 15 only)	X	X	X		
Blood chemistry ¹⁵	X	X ¹² (Day -6 only)	X	X	X (Day 15 only)	X	X	X		
